## STATISTICAL ANALYSIS

Initially, a review of the quality of the study data will be carried out: detection of errors in the coding, missing data and possible biases related to representativeness of the sample (for example, selection of subjects and loss in follow-up, among others).

Different descriptive statistics will be used to analyze the baseline characteristics (qualitative and quantitative variables) of the patients included in the study. For the categorical variables, such as the sociodemographic and clinical variables of the patients, they will be analyzed and represented by frequency tables (globally and by strata). For numerical variables, means and standard deviations will be calculated. Patients who leave the study will be described, including the characteristics of the patients and the reasons for the loss of follow-up.

The bivariate analysis will try to find the presence of a significant association between baseline cardiovascular risk and the score obtained in the cognitive and functional tests (MMSE 37, Trail Making Test, Semantic Verbal Fluency test, Six-Object Memory Recall Test, Clock drawing test, Pfeffer functional assessment scale). For this, the Pearson's Chi-square and Spearman statistical coefficients will be used, as appropriate.

Finally, multivariate analyses (multiple regression, analysis of covariance) will study the association between baseline cardiovascular risk (4 categories) and the psychometric and functional tests adjusted for relevant sociodemographic and clinical variables as potential confounding factors. Linear regression models of mixed effects (which take into account intrasubject variability when considering repeated measures) will be used, considering as a dependent variable the score obtained in each of the tests studied (one model for each scale) and as an independent, the cardiovascular risk basal (4 categories).

In addition, the reliable change in each of the tests will be analyzed to verify which clinically significant changes occur in subjects with high cardiovascular risk. The reliable change will be analyzed following the Hsu method, while the McSweeny and Duff method will be used to calculate simple and complex standards based in regression to estimate the cutoff points of change adjusted for age, sex and educational level. The data analysis will try to adhere to the standards for the diagnostic accuracy report. A statistically significant association will be considered when the contrast statistic has  $p < 0.05$ .

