**Cardiovascular Risk in People Older Than 55 Years and  
Cognitive Performance at 5 Years: an Estimation Model Based  
on Spanish Population. NEDICES-2-RISK study.**

NCT 03925844

Document Date: July 6, 2019

Dementia is unique in terms of prevalence, cost and impact. Any small advance in the prevention of dementia would benefit millions of people. Current data indicate that cardiovascular risk factors increase the risk of cognitive decline. The cardiovascular risk estimation by means of cardiovascular risk functions seems to be useful in the prediction of risk of cognitive deterioration. However, in the Spanish population, the incidence of coronary heart disease and stroke are lower than expected taking into account the cardiovascular risk factors.

The purpose of this study is to study the association between the cardiovascular risk of the study population, using the Framingham REGICOR and FRESCO cardiovascular risk functions, and the cognitive performance after 5 years of follow-up. The identification of individuals who have a high risk of cognitive decline in later years using predictive models of vascular risk would be a good approach to the prevention of cognitive impairment.

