## **OBJECTIVES**

### **Primary**

The main objective is to evaluate the association between cardiovascular risk, calculated with the Framingham REGICOR and FRESCO risk functions, and the cognitive decline after 5 years of follow-up in the NEDICES-2-RISK cohort.

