### Procedure

Patients who agree to participate and sign the informed consent will undergo a neuropsychological assessment (after 5 years of follow-up) with the same test battery as in the first evaluation (performed between 2014-2017) by trained interviewers and The clinical variables (morbidity and cardiovascular risk factors) and treatment variables will be collected through a clinical interview.

Anthropometric variables, as well as chronic diseases and medication will be collected by the patient's doctor. The rest of the information will be collected by interviewers. See Table 1.

Table 1. Variables and measurements collected during the study

	Variables collected at baseline	Variables collected after 5 years of follow-up
Social and demographic variables collected by interviewers: - Age - Gender - Marital status - Education - Profession	X X X X X	X X
Health related variables collected by primary care physicians: - Blood pressure - Cholesterol levels - Weight and height - Morbidity - Pharmacotherapeutic treatment	X X X X X	X X X X X
Variables on lifestyle and health status collected by interviewers: - Alcohol consumption - Caffeine consumption - Tobacco use - Physical activity - Mediterranean diet - EuroQoL 5D-3L - Quality of life measurement scales	X X X X X X	X X X X X X
Neuropsychological assessment carried out by interviewers: - CES-D scale - Word accentuation test - MMSE 37 - Instrumental activities of daily living, Pfeffer scale	X X X	X X X

 
- Semantic Verbal Fluency test
 
- Six-Object Memory Recall Test
 
- Trail Making test
 
- Clock-drawing test
 
	X	X
Exposure variables calculated by the research team:		

 
- Framingham REGICOR function
 
- FRESCO function
 
	X	X
	X	X

CES-D scale: Center for Epidemiologic Studies Depression Scale; MMSE-37: Mini Mental State Examination 37 item-version; FRESCO: Función de Riesgo Española de acontecimientos Coronarios y Otros; REGICOR: Registre Gironí del Cor

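### The repeated-measures model names no time or risk-by-time term, so its risk coefficient mixes the baseline gap with part of the change and does not measure the 5-year decline of the primary objective

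*Combined protocol and SAP*

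**What the plan says.** The primary objective (OBJECTIVES, Primary) is the association between cardiovascular risk and "the cognitive decline after 5 years of follow-up in the NEDICES-2-RISK cohort". The opening purpose statement describes the target differently, as "the cognitive performance after 5 years of follow-up". The Procedure section provides two cognitive assessments per patient, the second "with the same test battery as in the first evaluation".

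The STATISTICAL ANALYSIS section first states that "multivariate analyses (multiple regression, analysis of covariance) will study the association between baseline cardiovascular risk (4 categories) and the psychometric and functional tests", adjusted for sociodemographic and clinical confounders that it does not list. It then specifies linear mixed models for the repeated measures, with as "dependent variable the score obtained in each of the tests studied (one model for each scale) and as an independent, the cardiovascular risk basal" in four categories. For none of these models does it name visit or time, a risk-by-time interaction, a change-score outcome, or the baseline score as a covariate.

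As a further analysis, "the reliable change in each of the tests will be analyzed to verify which clinically significant changes occur in subjects with high cardiovascular risk", with regression-based cutoffs of change adjusted for age, sex and educational level.

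**The concern.** Decline is a difference between two visits. A model with the score as outcome and only baseline risk as named predictor compares the risk categories on their average level over the two visits. That average includes whatever difference existed at the 2014–2017 assessment.

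Three things are at stake:

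- A cross-sectional difference could be published as decline associated with cardiovascular risk.
- A real difference in decline could be missed, because it enters at part weight or is offset by an opposite baseline difference.
- Because the contrast that tests decline is not named, it can be chosen after the data are seen.

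**Working it through.** **Inputs from the documents.** Two visits with the same battery (Procedure); four baseline risk categories and a mixed model on scores (STATISTICAL ANALYSIS); 965 patients (Sample size); significance at p < 0.05. The documents give no SD, effect size, visit correlation, category split or expected loss, so there is no stated figure to reproduce.

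**Step 1: what the coefficient estimates.** For two risk categories, the gap is d0 at baseline and d0 + D at year 5. With complete pairs and a random intercept, the risk coefficient compares subject means:

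[d0 + (d0 + D)] / 2 = d0 + D/2

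A main effect of time leaves this unchanged. Baseline confounders turn d0 and D into adjusted values but do not separate them. The risk × time coefficient equals D.

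Numerical check on one simulated complete data set of 965 patients (assumed between-subject SD 4, residual SD 3): the baseline gap was −2.767891 and the difference in change −0.586613. The formula gives −2.767891 − 0.586613/2 = −3.061197 to rounding. The model as written returned −3.061197, both by generalised least squares and by a fitted mixed model. The interaction coefficient was −0.586613.

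**Step 2: illustrative size.** Assumptions: single-visit SD of 1 at both visits; correlation r from 0.5 to 0.8; linear gradient over the categories, with gaps quoted lowest to highest; no covariates; joint 3-df F test at 0.05.

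- Risk main effect: expectation d0 + D/2, variance (1 + r)/2.
- Risk × time: expectation D, variance 2(1 − r).
- Non-centrality: λ = n × v × gap² / variance, with 3 and n − 4 df, where v is the between-group variance of a unit gradient. For equal groups v = 0.1389.

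Example, d0 = 0.3, D = 0, r = 0.5: λ = 965 × 0.1389 × 0.09 / 0.75 = 16.08, so the risk test rejects 93.4% of the time (93.1% in 2000 simulations). At r = 0.8 the variance is 0.90, λ = 13.40, and the figure is 88.0%.

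| Scenario (n = 965) | Test | Equal groups | 40/35/15/10% groups |
|---|---|---|---|
| Same decline, baseline gap 0.3 SD | Risk | 88–93% | 77–84% |
| Same decline, baseline gap 0.2 SD | Risk | 51–60% | 40–47% |
| Same decline, baseline gap 0.1 SD | Risk | 15–17% | 12–14% |
| Any of the three above | Risk × time | 5% | 5% |
| No baseline gap, decline differs by 0.3 SD | Risk | 30–36% | 24–28% |
| No baseline gap, decline differs by 0.3 SD | Risk × time | 84% to over 99% | 72–99% |

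With 20% loss and completers only (965 × 0.8 = 772, equal groups), the last comparison becomes 25–29% against 74–99%.

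Cancellation: with d0 = +0.15 SD and D = −0.30 SD, the coefficient is 0.15 − 0.30/2 = 0. The risk test then rejects 5% of the time although decline differs.

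**Step 3: loss to follow-up.** The plan expects some, since it lists "selection of subjects and loss in follow-up, among others" among possible biases. If a fraction m is lost equally across groups and baseline-only patients are kept, the weight on D is 0.5c/(c + m), with c = 2(1 − m)/(1 + r).

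- m = 0.2: c = 1.067 to 0.889, weight 0.42 to 0.41.
- m = 0.3: c = 0.933 to 0.778, weight 0.38 to 0.36.

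The coefficient then leans further towards the baseline gap.

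**The case against.** The strongest reply is that the text is a verbal summary, not a model equation. Covariates are also absent from the mixed-model sentence although adjustment is promised just before it, so time may be implied by the reference to repeated measures. An analysis of covariance adjusted for baseline score would be a conventional analysis of decline, and the plan does not exclude it. Change is also addressed by the reliable-change analysis. On this view the fault is under-specification, and the figures above show a mechanism built on assumed inputs.

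Part of this stands. The sizes are illustrative, a 0.1 SD gap produces few false findings, covariate adjustment could change the baseline gap, and the cancellation case is constructed.

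The rest does not remove the problem. The plan explains the repeated-measures feature as handling within-subject variability, which is the role of the random effect. Even an implied time main effect would leave the risk coefficient as an average over visits. The covariance analysis is given neither an outcome visit nor a baseline-score covariate. The reliable-change analysis is introduced as an addition, refers to high-risk subjects, and states no test across the four categories.

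It can also be objected that one half is not a universal weight. An unstructured covariance would give another: (s1² − c)/(s1² + s2² − 2c), where s1 and s2 are the visit SDs and c their covariance. If the year-5 SD were 1.2 times baseline, this is 0.32 at correlation 0.5 and 0.08 at 0.8. The plan states no such structure. An ordinary random-intercept fit to complete pairs gives one half whatever the true visit variances. Under either structure the coefficient is not D.

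**Conclusion.** The concern holds: the model is wrong as written for the primary objective, and no stated analysis tests the four risk categories against change. That the risk coefficient does not isolate decline follows from the algebra and needs no assumed effect size. The weight of exactly one half requires a random-intercept fit to complete pairs, and it falls below one half if baseline-only patients are kept. The rejection rates rest on the assumed gaps, correlations, category splits and absence of covariates, and they are not predictions for this cohort. This must be fixed before analysis; confidence is high.

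**What to change.** Specify the primary model for each test as: score = risk category + time (visit or years since baseline) + risk category × time + named confounders + random subject intercept.

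- Name the joint 3-df risk × time test, or one pre-stated trend contrast, as the primary test of association with decline.
- Report the three category-specific differences in change as the estimates, and report the baseline risk effect separately as cross-sectional.
- If the analysis of covariance is kept, state its outcome and whether the baseline score is a covariate.

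Useful but optional: covariate × time terms for age, sex and education; change scores in the bivariate step; and a stated comparison of reliable change across the four categories.

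The cost is SAP wording only. The same battery is given at both visits, so no new data are needed.

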### **Secondary**

- (a) To describe the profile of patients according to their cardiovascular risk
- (b) To study the association between each cardiovascular risk factor in isolation and the cognitive decline after a 5-year follow-up
- (c) To study the association between calculated cardiovascular risk with the risk functions Framingham REGICOR and FRESCO and other non-neurological diseases
- (d) To analyze possible mediating effects between cardiovascular risk, cognitive decline and lifestyle
- (e) To investigate the effect of mediation of cognitive reserve indicators (verbal intelligence, education, occupation and lifestyle) on cognitive deterioration in different tests of the neuropsychological evaluation.

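### One unadjusted p < 0.05 rule covers every association, and secondary objectives (b) to (e) have neither an exploratory label nor control for the number of tests

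*Combined protocol and SAP*

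**What the plan says.** The only decision rule is the last sentence of the Statistical Analysis section: "A statistically significant association will be considered when the contrast statistic has" p < 0.05. It names no objective, test family or adjustment.

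Two of the secondary objectives imply several tests each:

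- Objective (b): "To study the association between each cardiovascular risk factor in isolation and the cognitive decline after a 5-year follow-up". The factors are not listed, and the measure of decline is not named.
- Objective (e) concerns mediation by "cognitive reserve indicators (verbal intelligence, education, occupation and lifestyle) on cognitive deterioration in different tests of the neuropsychological evaluation". That is four named indicators and an unstated number of tests.

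Table 1 (Procedure) lists "Blood pressure - Cholesterol levels - Weight and height" among the physician-collected variables and tobacco use among the lifestyle variables. The Statistical Analysis section names six outcome scales: "MMSE 37, Trail Making Test, Semantic Verbal Fluency test, Six-Object Memory Recall Test, Clock drawing test, Pfeffer functional assessment scale". Its mixed-effects analysis uses "one model for each scale", with overall baseline cardiovascular risk in four categories as the independent variable. No composite of the scales is defined. No model is described for the individual factors in (b) or for the mediation in (e).

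**The concern.** Objective (b) exists to say which individual risk factor goes with cognitive decline. Under the stated rule, any single factor-by-scale result with p < 0.05 counts as a statistically significant association, however many such results were examined. Suppose one factor is significant on one scale and nothing else is. The plan gives the reader no means of judging whether that is more than the chance yield of the search. The same applies to a single reserve indicator that appears to mediate change on one test under (e). Objectives (c) and (d) fall under the same rule.

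What is at stake is how far the secondary claims can be trusted. Data collection and the primary estimates are unaffected.

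**Working it through.** **Figure to reproduce.** There is none. The 0.05 is a chosen per-test threshold, and the document states no family-wise rate and no number of tests.

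**Inputs from the document.** Per-test level 0.05 (Statistical Analysis, last sentence; sidedness not stated, two-sided assumed). Six scales (Statistical Analysis). Four reserve indicators (objective (e)). Four candidate factors for (b): blood pressure, cholesterol, weight/height and tobacco (Table 1).

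**Assumptions.** That (b) uses these four factors. That each factor-scale pair gets one test. The correlations between test statistics. The document gives none of these. All null hypotheses are taken as true.

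**Method.** For k independent tests, P(at least one false positive) = 1 − 0.95^k, and the expected number of false positives is 0.05k. For correlated tests, I simulated sets of z statistics with a common correlation between factors and another between scales, and counted the sets in which any |z| exceeded 1.96.

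**Objective (b), four factors by six scales, k = 24**

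| Correlation between factors / between scales | P(at least one) |
|---|---|
| 0 / 0 | 1 − 0.95^24 = 71% |
| 0.1 / 0.3 | 67% |
| 0.2 / 0.3 | 66% |
| 0.3 / 0.5 | 58% |
| 0.5 / 0.7 | 44% |

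Expected false positives: 24 × 0.05 = 1.2 in every row. A single very high correlation of 0.8 among all 24 statistics would lower the probability to 24%. Leaving out the Pfeffer scale, which is functional rather than cognitive, gives k = 20 and 1 − 0.95^20 = 64% under independence, or 41% at 0.5 / 0.7.

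**Objective (b), one decline outcome, k = 4.** 1 − 0.95^4 = 18.6% under independence. By simulation, 18.0% at a factor correlation of 0.2 and 15.6% at 0.5. Hence about 15% to 19%.

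**Objective (e), four indicators by six scales, k = 24.** The rate depends on the mediation test. For illustration, take a rule that requires both the exposure-to-mediator and the mediator-to-outcome path to be significant, with independent tests:

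- Both paths null: 0.05² = 0.0025 per test, so 1 − 0.9975^24 = 5.8%.
- Only the four exposure-to-mediator paths null, with the other paths strong: 1 − 0.95^4 = 18.6%.
- Exposure-to-mediator paths real, all 24 mediator-to-outcome paths null: 1 − 0.95^24 = 71%.

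**Primary objective, for context.** Two risk functions by six scales, k = 12: 1 − 0.95^12 = 46% under independence, and 28% to 42% at correlations from 0.5 / 0.7 to 0.2 / 0.3.

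**The case against.** The strongest reply is that this is an observational cohort whose objectives are already split into one primary and several labelled secondary. Many statisticians would not adjust secondary analyses in such a study. The plan claims no family-wise rate of 0.05, so setting a family-wise probability against a per-test threshold does not show a promise broken. Nor does the plan say that a significant association is an established one. All of that stands, and it rules out demanding formal error control as the only remedy. It does not remove the problem: the document adopts an unrestricted significance rule and nowhere says that (b) to (e) are to be read differently from the primary objective.

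The second reply concerns the count. A reader might infer that (b) involves at least 24 tests. The document does not support that as a minimum. The one-model-per-scale wording belongs to the analysis of overall four-category risk, and (b) speaks only of cognitive decline. The 24 is an assumption. It is a reasonable one, because no single decline measure is defined, but the one-outcome reading has to be shown beside it.

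Third, the calculations take every null as true, whereas the introduction says that current data link cardiovascular risk factors with cognitive decline. Some significant results may therefore be real. The figures give the chance yield when there is nothing to find. They do not predict the proportion of false findings.

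**Conclusion.** The concern holds in a limited form. One unadjusted p < 0.05 rule applies to every association, with no exploratory label, ranking or multiplicity control for (b) to (e).

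For (b), the chance of at least one false significant association is about 44% to 67% with four factors, six scales and assumed moderate correlations (71% if independent), and about 15% to 19% with one decline outcome. Even the lowest of these is about three times the per-test level. For (e), the range of about 6% to 71% mainly reflects the missing mediation method.

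Three stronger readings are tempting and are not supported:

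- That chance findings in (b) are very probable. Several plausible scenarios lie below one half.
- That (e) carries a risk of the same size as (b). That cannot be known until the mediation test is specified.
- That keeping the p < 0.05 rule for the primary objective alone would leave that objective in order. Its two functions and six scales raise the same question.

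**What to change.** Add to the last paragraph of the Statistical Analysis section that objectives (b) to (e) are exploratory. They would be reported as estimates with 95% confidence intervals and the number of tests run, without claims of statistical significance.

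If the team wants to name individual factors under (b) or indicators under (e) as associated, the plan should first list the factors, the scales and the mediation method. It should then control the false discovery rate at 5% by Benjamini-Hochberg within each objective. The list has to come first, because the procedure cannot be applied to an undefined family.

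The cost is a few sentences and, on the second route, a simple p-value adjustment. No new data or patients are needed. The downside is that isolated secondary results with p just below 0.05 would no longer be called significant. In a 24-test family, the smallest p-value would have to reach 0.05/24 = 0.0021 if it were the only finding.

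Multiplicity in the primary objective needs its own decision and should not be treated as settled by this change.
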